6.8 Treatment exposure and compliance

Pharmacokinetic parameters (measures of treatment exposure) will be determined in all patients treated with LIK066, as detailed in [Section 8.7](#).

The investigator must promote compliance by instructing the patient to take the study treatment exactly as prescribed and by stating that compliance is necessary for the patient's safety and the validity of the study. The patient must also be instructed to contact the investigator if he/she is unable for any reason to take the study treatment as prescribed.

Compliance will be assessed by the Investigator and/or study personnel at each visit using pill counts and information provided by the patient. This information should be captured in the source document at each visit. All study treatment dispensed and returned must be recorded in the Drug Accountability Log.

6.9 Recommended treatment of adverse events

Treatment of AEs may be considered at the discretion of the Investigator. Medication used to treat AEs must be recorded on the Concomitant medications/Significant non-drug therapies CRF. In case of intolerable diarrhea, see SOM for guidelines on management of diarrhea.

6.10 Concomitant treatment

The investigator must instruct the subject to notify the study site about any new medications he/she takes after the subject was enrolled into the study.

All prescription medications, over-the-counter drugs and significant non-drug therapies (including physical therapy and blood transfusions) administered or taken within the timeframe defined in the entry criteria prior to the start of the study and during the study, must be recorded on the Concomitant medications/Significant non-drug therapies CRF.

Medication entries should be specific to trade name, the single dose and unit, the frequency and route of administration, the start and discontinuation date and the reason for therapy.

Each concomitant drug must be individually assessed against all exclusion criteria/prohibited medication. If in doubt, the investigator should contact Novartis before randomizing a subject or, if the subject is already enrolled, to determine if the subject should continue participation in the study.

7 Study completion and discontinuation

7.1 Study completion and post-study treatment

Each patient will be required to complete the study in its entirety and thereafter no further study treatment will be made available to them.

Study completion is defined as when the last patient completes their Study Completion visit, and any repeat assessments associated with this visit have been documented and followed-up appropriately by the Investigator, or in the event of an early study termination decision, the date of that decision.

All patients should have a safety follow-up call conducted 30 days after last visit. The information collected is kept as source documentation. All SAEs reported during this time period must be reported as described in [Section 9.2](#) and the Site Operations Manual. Documentation of attempts to contact the patient should be recorded in the source documentation.

7.2 Discontinuation of study treatment

Discontinuation of study treatment for a patient occurs when study treatment is stopped earlier than the protocol planned duration. Discontinuation of study treatment can be decided by either the subject or the investigator.

Study treatment must be discontinued under the following circumstances:

- Patient decision - patients may choose to discontinue study treatment for any reason at any time.
- The investigator believes that continuation would negatively impact the safety of the patient or the risk/benefit ratio of trial participation.
- Any protocol deviation that results in a significant risk to the patient's safety
- Pregnancy (see [Section 8.6](#) (Safety) and [Section 9.6](#) (Pregnancy reporting))
- Discontinuation may be considered when patients have to be treated by prohibited medications on a case by case basis.

- Use of prohibited treatment as per recommendations in [Table 5-1](#)
- Hypersensitivity (CTCAE grade 2 or higher) reaction to LIK066 requiring intervention.
- Clinically significant diarrhea, suspected to be related to the study drug and not responsive to recommended management per SOM that may put the patient at risk (identified by investigator after consultation with the sponsor)
- Symptomatic orthostasis confirmed by repeated orthostatic blood pressure changes (more than a 20 mmHg drop in systolic or 10 mmHg drop in diastolic blood pressure and increase in heart rate >20 bpm (compared to sitting results) when blood pressure and pulse are taken after at least 3 minutes (standing)
- Clinically significant urinary tract or genitourinary infections, at the discretion of the investigator and consultation with the sponsor
- Clinically symptomatic hypoglycemia confirmed by repeated blood glucose levels (<56 mg/dL)
- Ketoacidosis (symptoms of ketoacidosis include nausea, vomiting, abdominal pain, unusual tiredness and trouble breathing) confirmed by blood pH and ketones.
- For ALT, AST, total bilirubin and/or alkaline phosphatase elevations mandating study treatment discontinuations, please refer to [Section 9.3](#) and [Table 9-1](#) and [Table 9-2](#) for further instructions and monitoring. Of note, ALT and AST are abnormal at baseline in this study. Thus only elevation to >2X of the baseline value will trigger events listed in [Section 9.3](#).
- Adverse events, abnormal laboratory values or abnormal test result that indicate a safety risk to the patient, in the opinion of the investigator

Commercially Confidential Information

Discontinuation of study treatment and patient withdrawal may occur, under the following circumstances:

- Any protocol deviation that results in a significant risk to the patient's safety in the opinion of the investigator.
- If continuation in the study is deemed detrimental to the patient's well-being in the opinion of the investigator.

The appropriate personnel from the study site and Novartis (including the CTT, medically qualified representatives of the Sponsor, and the investigator) will assess whether study treatment should be discontinued for any patient whose treatment code has been broken inadvertently for any reason.

If discontinuation of study treatment occurs, investigator must determine the primary reason for the patient's premature discontinuation of study treatment and record this information on the Dosage Administration CRF.

Patients who discontinue study treatment or who decide they do not wish to participate in the study further should NOT be considered withdrawn from the study UNLESS they withdraw their consent (see [Section 7.3](#), Withdrawal of Informed Consent). Where possible, they should return for the assessments as indicated in the assessment table. If they fail to return for these assessments for unknown reasons, every effort (e.g. telephone, e-mail, letter) should be made to contact the patient/pre-designated contact as specified in [Section 7.4](#) (Lost to follow-up). This contact should preferably be done according to the study visit schedule. The investigator must also contact the IRT to register the subject's discontinuation from study treatment.

The investigator must also contact the IRT to register the patients's discontinuation from study treatment.

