8. Current or history of significant alcohol consumption for a period of more than 3 consecutive months within 1 year prior to screening (significant alcohol consumption is defined as more than 20 g/day in females and more than 30 g/day in males, on average).

Commercially Confidential Information

10. Clinical evidence of hepatic decompensation or severe liver impairment as defined by the presence of any of the following abnormalities:

- Serum albumin < 32 g/L
- INR > 1.3
- Direct bilirubin > 13 mg/L
- ALT or AST > 8× ULN
- Alkaline Phosphatase > 3 × ULN
- History of esophageal varices, ascites or hepatic encephalopathy
- Splenomegaly

Commercially Confidential Information

12. Presence of cirrhosis on liver biopsy or clinical diagnosis of cirrhosis.

Commercially Confidential Information

16. Patients taking medications prohibited by the protocol. See [Section 5.2](#) for further details.

17. For those patients that have had a previous liver biopsy: Significant weight loss (>15%) or change in clinical status (in the opinion of the investigator) since the diagnostic liver biopsy to screening (refer to [Section 4.1 #3](#)).

Commercially Confidential Information

22. History of non-alcohol drug abuse within the 12 months prior to dosing, or evidence of such abuse as indicated by the laboratory assays conducted during screening and baseline.

23. Women of child-bearing potential, defined as all women physiologically capable of becoming pregnant, **unless** they are using basic methods of contraception during dosing and for 5 days (approximately 5 times the terminal half life) after stopping study medication. **Basic contraception methods include:**

- Total abstinence (when this is in line with the preferred and usual lifestyle of the subject. Periodic abstinence (e.g., calendar, ovulation, symptothermal, post-ovulation methods) and withdrawal are not acceptable methods of contraception
- Female sterilization (have had surgical bilateral oophorectomy with or without hysterectomy) or tubal ligation at least six weeks before taking study treatment. In case of oophorectomy alone, only when the reproductive status of the woman has been confirmed by follow up hormone level assessment
- Male sterilization (at least 6 months prior to screening). For female subjects on the study the vasectomized male partner should be the sole partner for that subject
- Barrier methods of contraception: Condom or Occlusive cap.

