- Use of oral (estrogen and progesterone), injected or implanted combined hormonal methods of contraception or placement of an intrauterine device (IUD) or intrauterine system (IUS), or other forms of hormonal contraception that have comparable efficacy (failure rate <1%), for example hormone vaginal ring or transdermal hormone contraception. In case of use of oral contraception women should have been stable on the same pill for a minimum of 3 months before taking study treatment.

Women are considered post-menopausal and not of child bearing potential if they have had 12 months of natural (spontaneous) amenorrhea with an appropriate clinical profile (e.g. age appropriate, history of vasomotor symptoms) or have had surgical bilateral oophorectomy (with or without hysterectomy), total hysterectomy or tubal ligation at least six weeks ago. In the case of oophorectomy alone, only when the reproductive status of the woman has been confirmed by follow up hormone level assessment is she considered not of child bearing potential.

Commercially Confidential Information

Commercially Confidential Information

The investigator must ensure that all patients being considered for the study meet the above eligibility criteria.

Patient selection is to be established by checking through all eligibility criteria at screening and baseline. A relevant record (e.g. checklist) of the eligibility criteria must be stored with the source documentation at the study site.

Provided patients meet all other eligibility criteria, patients with a single lab value outside of the allowable range may be considered eligible for enrolment, as long as the abnormal lab value is within 10% of the allowable value. Platelets and eGFR values must always fall inside the allowable range as listed in the inclusion and exclusion criteria.

No additional exclusions may be applied by the investigator, in order to ensure that the study population will be representative of all eligible patients.

5 Restrictions for Study Subjects

For the duration of the study, the subjects should be informed and reminded of the restrictions outlined in this section.

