9.3 Liver safety monitoring

To ensure patient safety and enhance reliability in determining the hepatotoxic potential of an investigational drug, a standardized process for identification, monitoring and evaluation of liver events has to be followed. The following two categories of laboratory abnormalities and AEs have to be considered during the course of the study 1) Liver laboratory triggers which will require repeated assessments of the abnormal laboratory parameter and 2) Liver events which will require close observation, follow up monitoring, and the completion of the standard base liver eCRF pages.

Please refer to [Table 9-1](#) for complete definitions of liver events.

Table 9-1 Liver Event Definitions

	Definition/ threshold
Liver laboratory triggers	
 ALT or AST $\geq 2 \times$ baseline value $1.5 \times \text{ULN} < \text{TBL} < 2 \times \text{ULN}$
Liver events	
 ALT or AST $> 5 \times \text{ULN}$ ALP $> 2 \times \text{ULN}$ (in the absence of known bone pathology) TBL $> 2 \times \text{ULN}$ (in the absence of known Gilbert syndrome) ALT or AST $> 3 \times \text{ULN}$ and INR $> 1.5 \text{ ULN}$ Potential Hy's Law cases (defined as ALT or AST $> 3 \times \text{ULN}$ and TBL $> 2 \times \text{ULN}$ [mainly conjugated fraction] without notable increase in ALP to $> 2 \times \text{ULN}$) Any clinical event of jaundice (or equivalent term) ALT or AST $> 3 \times \text{ULN}$ accompanied by (general) malaise, fatigue, abdominal pain, nausea, or vomiting, or rash with eosinophilia Any adverse event potentially indicative of a liver toxicity*

*These events cover the following: hepatic failure, fibrosis and cirrhosis, and other liver damage-related conditions; the non-infectious hepatitis; the benign, malignant and unspecified liver neoplasms

TBL: total bilirubin; ULN: upper limit of normal

Follow-up of liver events

Every liver event defined in [Table 9-1](#) should be followed up by the investigator or designated personnel at the trial site, as summarized below. Additional details on actions required in case of liver events are outlined in [Table 9-2](#).

For liver laboratory triggers

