- Repeating liver chemistry tests (ALT, AST, TBL, PT/INR, ALP and GGT) to confirm elevation within the next 7 days. If any of the lab tests described in [Table 9-1](#) are abnormal, all tests should be repeated. These liver chemistry repeats should preferentially be performed using the central laboratory, with the results provided via the standard electronic transfer. If results will not be available from the central laboratory within 24 hours, then the repeats can also be performed at a local laboratory to monitor the safety of the patient. If a liver event is subsequently reported, any local liver chemistry tests previously conducted that are associated with this event should have results reported on the unscheduled local laboratory CRF.
- If the initial elevation is confirmed, close observation of the patient will be initiated, including consideration of treatment interruption if deemed appropriate.

For Liver Events

- Discontinuation of the investigational drug (refer to [Section 7.2](#) (Discontinuation of study treatment), if appropriate)
- Hospitalization of the patient if appropriate
- Causality assessment of the liver event

Thorough follow-up of the liver event should include:

- Repeating liver chemistry tests to confirm elevation as appropriate. Testing should include PT/INR ALT, AST, ALP, and GGT. If total bilirubin is elevated > 2 x ULN, fractionation into direct and indirect bilirubin is required. To rule out muscular origin of transaminase elevations, CPK should be measured along with liver chemistry tests. Frequency of retesting should be done once a week if abnormalities stabilize or the study drug has been discontinued and the subject is asymptomatic. Retesting should be continued up to resolution or stabilization as described above.
- Obtaining a more detailed history of symptoms and prior or concurrent diseases.
- Obtaining a history of concomitant drug use (including nonprescription medications and herbal and dietary supplement preparations), alcohol use, recreational drug use, and special diets.
- Exclusion of underlying liver disease, as specified in [Table 9-3](#).
- Imaging such as abdominal US, CT or MRI, as deemed appropriate by the investigator
- Obtaining a history of exposure to environmental chemical agents.
- Considering gastroenterology or hepatology consultation.

All follow-up information, and the procedures performed must be recorded as appropriate in the CRF.

Table 9-2 Actions required for Liver Events

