Criteria	Actions required	Follow-up monitoring
Potential Hy's Law case ^a	
 • Discontinue the study drug immediately • Hospitalize, if clinically appropriate • Establish causality • Complete liver CRF 	ALT, AST, TBL, Alb, PT/INR, ALP and GGT until resolution ^c (frequency at investigator discretion)
ALT or AST		
> 10 × ULN	
 • Repeat within 48 hr • If elevation persists, discontinue drug • Hospitalize if clinically appropriate • Establish causality • Complete liver CRF 	ALT, AST, TBL, Alb, PT/INR, ALP and GGT until resolution ^c (frequency at investigator discretion)

Criteria	Actions required	Follow-up monitoring
> 3 × ULN AND INR > 1.5	
 Discontinue the study drug immediately Hospitalize, if clinically appropriate Establish causality Complete liver CRF 	ALT, AST, TBL, Alb, PT/INR, ALP and GGT until resolution ^c (frequency at investigator discretion)
> 5 to ≤ 10 × ULN	
 Repeat LFT within 1 week If elevation persists continue follow up, If elevation persists for more than 3 weeks discontinue drug Establish causality Complete liver CRF 	ALT, AST, TBL, Alb, PT/INR, ALP and GGT until resolution ^c (frequency at investigator discretion)
> 3 × ULN AND accompanied by symptoms ^b	
 Discontinue the study drug immediately Hospitalize if clinically appropriate Establish causality Complete liver CRF 	ALT, AST, TBL, Alb, PT/INR, ALP and GGT until resolution ^c (frequency at investigator discretion)
> 3 to ≤ 5 × ULN if normal baseline or >2 × baseline if elevated before drug exposure (patient is asymptomatic)	
 Repeat LFT within 1 week If elevation is confirmed, initiate close observation of the subject 	Investigator discretion Monitor LFT within 1 to 4 weeks
ALP (isolated)		
> 2 × ULN if normal baseline (in the absence of known bone pathology)	
 Repeat LFT within 48 hours If elevation persists, establish causality Complete liver CRF 	Investigator discretion Monitor LFT within 1 to 4 weeks or at next visit
TBL (isolated)		

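### Protocol 7.2 makes liver events conditional on ALT/AST above twice baseline, while Tables 9-1 and 9-2 set the stops at fixed multiples of ULN; no visible text says which rule prevails

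*Protocol*

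**What the plan says.** Protocol 7.2 lists the circumstances in which study drug must be stopped. Its liver bullet points to Section 9.3 and Tables 9-1 and 9-2, remarks that ALT and AST are already abnormal at baseline, and continues: "Thus only elevation to >2X of the baseline value will trigger events listed in" Section 9.3.

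Section 9.3 separates two categories. The first is "Liver laboratory triggers which will require repeated assessments of the abnormal laboratory parameter"; Table 9-1 puts ALT or AST at or above twice baseline here. The second is liver events, whose numerical ALT/AST criteria in Table 9-1 are all multiples of ULN. For liver events, 9.3 sends the stop decision back to 7.2: "Discontinuation of the investigational drug (refer to" that section, if appropriate).

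The ALT/AST rows of Table 9-2 that stop drug carry no baseline condition:

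- Potential Hy's Law (ALT/AST >3×ULN with TBL >2×ULN): stop at once.
- "> 3 × ULN AND INR > 1.5": stop at once.
- >3×ULN with symptoms: stop at once.
- >10×ULN: repeat within 48 hours, stop if it persists.
- >5 to ≤10×ULN: "If elevation persists for more than 3 weeks discontinue drug".

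The only ALT/AST row adjusted for an abnormal baseline, ">2 × baseline if elevated before drug exposure (patient is asymptomatic"), asks for a repeat and close observation, not a stop.

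Exclusion 10 in 4.2 removes patients with "ALT or AST > 8× ULN", so entry up to 8×ULN is allowed. Section 4.2 also tolerates one out-of-range laboratory value "as long as the abnormal lab value is within 10% of the allowable value", exempting only platelets and eGFR.

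On holds, 6.6 permits no interruption. Yet 8.6.7 (positive urine pregnancy test), 9.8.3 (symptomatic orthostasis) and Table 9-4 (creatinine rise >50% that cannot be confirmed in time) each require one, and 9.3 allows one after a confirmed liver trigger.

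**The concern.** The note says only, and it says events, the word that 9.3 uses for the category that leads to stopping. A site that takes it at face value applies a bar of twice baseline to rows that Table 9-2 states without one. The same laboratory report can then be a stop under Table 9-2 and not a stop under 7.2. Because 7.2 and 9.3 refer to each other, neither settles the matter. The stake is patient safety in the rows meant to catch serious drug-induced liver injury.

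The note cannot be applied uniformly in any case, because neither 7.2 nor 9.3 says which draw is the baseline. The efficacy definitions do not help: Protocol 11.4.1 averages V101 and V201, while SAP 6.1.1 averages V1 and V101.

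**Working it through.** The plan gives no figure to reproduce here; the check is threshold arithmetic. Let b be baseline ALT or AST in multiples of ULN.

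**Inputs.** Bar in 7.2: above 2b. Fixed thresholds T in Tables 9-1 and 9-2: 3, 5 and 10×ULN. Entry limit in 4.2: 8×ULN, or 8 × 1.1 = 8.8×ULN with the single-value tolerance.

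**Formula.** The literal bar overrides a fixed threshold T when 2b > T, that is, b > T/2.

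- T = 3 (Hy's Law, INR and symptom rows): b > 1.5
- T = 5: b > 2.5
- T = 10: b > 5

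All three ranges can be enrolled. Readings above T and up to 2b meet the table but not the 7.2 bar:

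| b (×ULN) | 7.2 bar 2b | Window above 3×ULN | Window above 10×ULN (width 2b − 10) |
|---|---|---|---|
| 1.5 | 3 | none | none |
| 2 | 4 | 3 to 4 | none |
| 5 | 10 | 3 to 10 | none |
| 6 | 12 | 3 to 12 | 10 to 12 (2) |
| 7 | 14 | 3 to 14 | 10 to 14 (4) |
| 8 | 16 | 3 to 16 | 10 to 16 (6) |
| 8.8 | 17.6 | 3 to 17.6 | 10 to 17.6 (7.6) |

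**Example 1.** b = 2, ALT 3.5×ULN, TBL 2.2×ULN, ALP normal. The Hy's Law row stops drug immediately (3.5 > 3 and 2.2 > 2). The 7.2 bar is 4×ULN and is not met. The note names only ALT and AST, so TBL >2×ULN remains a liver event under Table 9-1. The isolated-TBL row of Table 9-2, if applied, repeats within 48 hours and stops if the rise persists. The cost is mainly that delay.

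**Example 2.** b = 6, ALT 11×ULN, confirmed. Table 9-2 stops drug (11 > 10). The 7.2 bar is 12×ULN and is not met. No other mandatory stop based on ALT/AST alone lies behind that row.

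**Can these arise at planned visits?** ALT and TBL are in the same chemistry panel (8.6.3), visible in Table 8-1 on Days 7, 14, 28, 56 and 84, so yes. INR differs: the coagulation panel is visible only at Screening, Baseline and EOS. On treatment, INR comes mainly from the repeat tests that 9.3 orders after a trigger. If the trigger was ALT/AST at twice baseline, the 7.2 bar is already met, apart from exact equality.

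**In IU/L.** The documents do not give ULN. Assuming 30 to 55 IU/L, 1.5×ULN is 45 to 82.5 and 5×ULN is 150 to 275. The ALT entry floors are 50 (males) and 35 (females). At ULN 30, every male whose baseline stays at or above his floor exceeds 1.5×ULN; at ULN 55 the threshold lies well above both floors. The number of patients in either range is not given.

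**The case against.** The best defence is that the literal reading is not the natural one. The 7.2 bullet first sends the site to the tables and adds the twice-baseline remark only as a note. Both tables contain an entry that matches it: the laboratory trigger in Table 9-1 and the asymptomatic observation row in Table 9-2. Table 9-2 also orders an immediate stop for Hy's Law in plain terms. That may well be what the sponsor meant, and the fix below adopts it. But the text says events, and nothing visible confirms the narrower meaning.

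A reader might infer that the protocol switches off its Hy's Law protection. The documents do not support that. Table 9-1 lists TBL >2×ULN as a liver event in its own right, without the isolated or normal-baseline limits of the Table 9-2 row, and 9.3 attaches discontinuation, if appropriate, to liver events. Jaundice stops drug immediately. Two 7.2 bullets require a stop when the investigator sees a safety risk. At study level, the Grade 3 hold in 7.5 excludes ALT elevation, but the hold for a related Grade 4 event and the sponsor's unblinded monitoring remain.

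It also stands that the INR row is rarely affected and that the >10×ULN gap needs a baseline above 5×ULN.

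A reader might likewise infer from 6.6 that the safety holds are forbidden. The specific instructions elsewhere probably govern, so this is a clarification and adds no weight to the liver point.

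**Conclusion.** The two rules conflict as written and should be reconciled. Read literally, 7.2 raises the ALT/AST part of the Hy's Law and INR stops for baselines above 1.5×ULN, and the >10×ULN stop for baselines above 5×ULN. For Hy's Law the main consequence is a delay of up to a 48-hour repeat. For >10×ULN it is a window of 2 to 6×ULN at baselines of 6 to 8×ULN (7.6 at 8.8×ULN), in an unknown and probably small number of patients.

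It would go too far to say that the plan clearly stops stable patients who enter at >5 to 8×ULN. That happens after more than 3 weeks only where a site follows Table 9-2 and disregards the note; it is the other side of the same ambiguity. Nor do the documents show that the >5 to ≤10×ULN row ought to be moved to twice baseline.

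The conclusion rests on the visible text. Text after the 7.2 list and some exclusion criteria are redacted, so a further condition cannot be ruled out.

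**What to change.** Amend the protocol wording:

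1. In 7.2, state that the Hy's Law, >3×ULN with INR >1.5, and >10×ULN stops in Table 9-2 apply regardless of baseline, and that the >2×-baseline note applies only to the laboratory trigger and the asymptomatic observation row.
2. Name the draw used as safety baseline, for example V101 or the V1/V101 mean. No Day 1 chemistry sample is visible in Table 8-1, and Section 3.1 wants baseline safety results before first dosing, so V201 is a poor choice unless a Day 1 ALT sample is confirmed.
3. Have the sponsor decide, and write down, whether the >5 to ≤10×ULN row and the >3×ULN-with-symptoms row carry a baseline condition. This is a clinical choice. For the first row, adding the condition relaxes Table 9-2 for baselines above 2.5×ULN: at baseline 4×ULN, an ALT of 7×ULN lasting over 3 weeks would no longer stop drug, because the bar is 8×ULN. Above 5×ULN the row would cease to act. Leaving the condition out stops stable patients who enter at >5 to 8×ULN after 3 weeks. For the symptom row, the condition relaxes the stop for baselines above 1.5×ULN.
4. In 6.6, add: except safety holds specified in 8.6.7, 9.3, 9.8.3 and Table 9-4.

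Cost: an amendment, with no new procedures, samples or patients. The downside of item 1 is that a patient entering at 8×ULN stops at a confirmed rise of just over 10/8 = 1.25-fold (10/8.8 = 1.14-fold at 8.8×ULN).
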